5.3.5 Etoposide Dose Modifications

- **Dose reductions:** For non-hematologic grade 3 and 4 AEs (except for nausea and vomiting as well as AEs unrelated to treatment) the dose should be reduced according to the Etoposide Dose Level Table at the discretion of the investigator. Dose reductions for treatment day (or within 2 days of treatment) ANC and platelet counts should also be made according to the Dose Level Table below. Each dose reduction will be a 20% reduction from the prior level.
- **Discontinuation:** Also, except for nausea and vomiting, if any of the same non-hematologic grade 3 and 4 AEs that are at least possibly related to study treatment recur after reduction for that AE, then etoposide will be stopped.

Etoposide Dose Level Table	
Dose Level	Dose in mg/m ² (days 1-3)
0	100

Etoposide Dose Level Table	
-1	80
-2	64

*Note this is a 20% dose reduction with each dose level.

5.3.5.1 Hematologic Toxicity

ANC (/mm ³)		Platelets (/mm ³)	Modification
< 1500/mm ³	and/or	< 100,000/mm ³	Hold until ANC \geq 1500/mm ³ and platelets are \geq 100,000/mm ³ , resume at 20% dose reduction*
\geq 1500/mm ³	and	\geq 100,000/mm ³	No dose modification

*This table applies to day of treatment (or within 2 days of treatment) hematologic toxicities.

*If ANC and platelet count recover within one week, resume therapy at 100%. If greater than 7 days to recovery, upon recovery to ANC \geq 1,500/mm³ and platelets to \geq 100,000/mm³, the dose level -1 will be administered (80 mg/m²). Discontinue etoposide dose if patients do not recover within \leq 3 weeks. If patient was already receiving Etoposide at the -1 dose level, reduce to the -2 dose (64 mg/m²).

If already receiving treatment at the -1 dose level, upon recovery to ANC \geq 1,500/mm³ and platelets to \geq 100,000/mm³, the dose level -2 will be administered (64 mg/m²). Discontinue dose if patients do not recover within \leq 3 weeks. If patient was already receiving Etoposide at the -2 dose level, treatment should be discontinued.

Neutropenia or Febrile Neutropenia

For nadir neutropenia in the absence of fever or with fever that is successfully treated by oral antibiotics, there will be no dose adjustment. Filgrastim, sargramostim, or pegfilgrastim are allowed and should be administered according to ASCO guidelines (54). For treatment delays due to chemotherapy toxicities of more than 7 days, Etoposide should be dose-reduced according to the Etoposide Dose Level Table for all subsequent cycles of chemotherapy. For neutropenic fever (ANC < 500/mm³) and temperature $>$ 100.5F) requiring intravenous antibiotics, the doses of all chemotherapy drugs (cisplatin and etoposide) should be reduced by one dose level according to the Etoposide Dose Level Table and the Cisplatin Dose Level Table for the next cycle and all subsequent cycles. If counts to not recover within 4 weeks, discontinue all protocol therapy.

Thrombocytopenia

For grade 4 nadir platelet count decrease (thrombocytopenia) (platelets < 25,000/mm³), the dose of Etoposide should be reduced by one dose level according to the Etoposide Dose Level Table for the next cycle and for all subsequent cycles of chemotherapy. If counts do not recover within 4 weeks, discontinue all protocol therapy.

Anemia

No dose reduction will be made for anemia. Patients should be supported per the treating physician's discretion. The use of blood transfusions for anemia will be allowed as indicated. The use of erythropoietin stimulating agents is not permitted.

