5.3 Dose Modifications

5.3.1 General

Dose reductions will be based on current dose. If dose reduction is required, reduction is permanent. Missed doses will not be made up. No dose escalation is permitted for any of the study drugs.

Dose will be modified for all drugs if there is $\geq 10\%$ change in patient's weight while on study. For oral agents, particularly capecitabine, a new dose calculation may result in the same number of pills to be administered due to rounding issues.

Doses will be determined according to (1) non-hematologic AEs during the previous cycle, as well as (2) the lowest ANC and platelet counts during that cycle.

Patients may receive **a maximum of two** dose reductions per agent. If a third reduction is required, the patient should discontinue all protocol treatment. However, for Arm A, patients may discontinue one agent due to toxicity and continue the other on-study.

If different percentages of dose reductions for a specific drug are required because of two different types of toxicities, the greater percentage dose reduction should be undertaken.

AEs determined to be unrelated to study treatment will not require dose reduction.

NOTE: If patients have been off study treatment ≥ 4 weeks of next planned cycle start date, patients must discontinue protocol treatment.

NOTE: Starting cycles early is prohibited due to safety purposes.

All toxicity grades below are described using the NCI Common Terminology Criteria for Adverse Events (CTCAE) version 4.0.

All appropriate treatment areas should have access to a copy of the CTCAE version 4.0. A copy of the CTCAE version 4.0 can be downloaded from the CTEP website (<http://ctep.cancer.gov>).

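### For a blood-count hold of 7 days or less, section 5.3.5.1 leaves the next etoposide dose unsettled for a patient already at level -1 or -2

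*Combined protocol and SAP*

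**What the plan says.** All references are to the combined protocol and SAP.

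- **5.3.5.1, table cell.** If the treatment-day ANC is below 1500/mm³ or platelets are below 100,000/mm³, etoposide is held until both recover. The instruction is then "resume at 20% dose reduction", marked with an asterisk.
- **5.3.5.1, asterisked notes.** Two notes carry the asterisk. One sets the scope: "This table applies to day of treatment (or within 2 days of treatment) hematologic toxicities". The other splits by recovery time. For the short branch it says "If ANC and platelet count recover within one week, resume therapy at 100"%. The long branch opens "If greater than 7 days to recovery, upon recovery to ANC" and leads to level -1 (80 mg/m²), with a 3-week limit. The note ends with "If patient was already receiving Etoposide at the -1 dose level, reduce to the -2 dose (64 mg/m²)".
- **5.3.5.1, next paragraph, no asterisk.** It opens "If already receiving treatment at the -1 dose level, upon recovery to ANC", gives level -2 (64 mg/m²) with the same 3-week limit, and closes "If patient was already receiving Etoposide at the -2 dose level, treatment should be discontinued". It mentions no recovery time other than that limit.
- **5.3.5.1, later neutropenia text.** Etoposide is reduced after treatment delays of more than 7 days.
- **5.3.5.** Each reduction is 20% from the prior level. Reductions for treatment-day counts follow the dose level table, and no recovery time is mentioned.
- **5.3.1.** "No dose escalation is permitted for any of the study drugs". Reductions are permanent and based on the current dose. At most two are allowed per agent, and a third ends all protocol treatment.

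**The concern.** The one-week rule is stated once, with no limit on the patient's current level. The rules for patients already at -1 or -2 are stated without a recovery time. Both can be read to cover a reduced patient whose counts recover in, say, 3 days, and they lead to different actions. The percentage in the one-week rule also has no reference dose beside it.

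Etoposide belongs to Arm B, the comparator for the primary progression-free survival test, planned at 39 eligible patients per arm (9.2). Sites that follow the text in good faith could keep, reduce or stop control-arm etoposide for the same event. That bears on patient safety and on how uniformly the comparator is delivered.

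**Working it through.** **Dose levels.** The table in 5.3.5 gives 100, 80 and 64 mg/m². Taking 20% off the prior level reproduces it: 100 × 0.8 = 80 and 80 × 0.8 = 64. One further step would be 64 × 0.8 = 51.2 mg/m², which is not a listed level.

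**Each instruction applied literally to a hold of 7 days or less:**

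| Current level | Table cell without its note | One-week note (100% of current dose) | Level-specific sentences, if they cover any hold |
|---|---|---|---|
| 0 (100 mg/m²) | 80 | 100 | none |
| -1 (80 mg/m²) | 64 | 80 | 64 |
| -2 (64 mg/m²) | 51.2, unlisted; a third reduction, so stop under 5.3.1 | 64 | stop |

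**Level 0.** The cell carries the asterisk that leads to the one-week note, so the note qualifies the cell: recovery within a week means no reduction, longer recovery means level -1. The later sentence on delays of more than 7 days makes the same split. The remaining blemishes are that one asterisk serves two notes and that 5.3.5 is silent on recovery time.

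**Level -1.** The one-week note gives 80 mg/m². The level-specific sentences give 64 mg/m². The gap is 80 − 64 = 16 mg/m² per day. Over days 1-3 it is 3 × 80 = 240 against 3 × 64 = 192 mg/m² per cycle, or 20% less.

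**Level -2.** The one-week note gives 64 mg/m² (192 mg/m² per cycle). The closing sentence of the unasterisked paragraph gives none.

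**Does the text say which branch the level-specific sentences belong to?** Their position, after the more-than-7-days sentence, suggests the longer branch. Three features point the other way:

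1. The unasterisked paragraph has its own recovery trigger. It repeats the step from -1 to -2 that the note has just given, so if it is confined to the longer branch that half adds nothing.
2. The temozolomide footnotes in 5.3.3.1 move patients from -1 to -2, and stop them at -2, with no 7-day split. A site could read the etoposide paragraph in the same way.
3. The general rule in 5.3.5 for treatment-day counts has no time condition.

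**Are holds near 7 days foreseeable?** Section 8.4.11.1 puts the carboplatin nadir at about day 21, with recovery by day 28-30. With a 21-day cycle the next dose falls on day 21 or 22, depending on whether counting starts at 0 or 1. Recovery would then come between 28 − 22 = 6 and 30 − 21 = 9 days later, on either side of the 7-day line. This shows plausibility for carboplatin, not a rate.

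**The case against.** The strongest reply is that 5.3.5.1 contains one coherent rule. The asterisk ties the 7-day split to the cell. The sentences for -1 and -2 follow the more-than-7-days branch, reuse its recovery wording and 3-week limit, and can be read as its continuation one level down. The later sentence on delays of more than 7 days fits this. On that reading the text omits a repeated condition and contradicts nothing.

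This disposes of the level 0 case. It makes the -1 and -2 cases an ambiguity rather than a proven contradiction, but it does not remove the ambiguity, because the condition has to be supplied by the reader.

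A reader might infer more in three respects, and the documents do not support it:

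- **Four incompatible doses after any short hold** (20% cut, full dose, next level down, stop). Under 5.3.5 a 20% cut and one level down are the same step. The sentence telling sites to stop concerns only level -2. No patient faces all four.
- **A return to 100 mg/m² for a reduced patient.** The reference dose is not named in place, but 5.3.1 makes reductions permanent and bars escalation, which implies the current dose.
- **A demonstrated distortion of the primary comparison.** The documents give no frequency of short holds and no link from etoposide dose to progression-free survival.

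**Conclusion.** The point holds for patients already at level -1 or -2 whose counts recover within 7 days. At -1 the text supports 80 or 64 mg/m², a 20% difference. At -2 it supports continuing at 64 mg/m² or stopping. This assumes that 100% means the current dose, as 5.3.1 implies, and that the level-specific sentences can fairly be read without a 7-day condition. If the sponsor intended them only for longer recovery, the defect is a missing condition.

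At level 0 the point is one of clarity. How many patients would be affected, and any effect on progression-free survival, cannot be quantified from the documents. The reconciliation is still worth making, because the same event could lead sites to continue, reduce or stop part of the control regimen.

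**What to change.** Reconcile the table cell, the asterisked note, the paragraph after it and the general rule in 5.3.5. For each current level (0, -1 and -2), state one consequence for recovery within 7 days and one for longer recovery. Name the dose to which 100% refers, consistently with 5.3.1. Use separate markers for the scope note and the recovery note. The sponsor decides which consequence applies in each case.

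The cost is protocol wording in an amendment. It adds no patients, visits or procedures.

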5.3.4 Cisplatin or Carboplatin Dose Modifications

- **Dose reductions:** For non-hematologic grade 3 and 4 AEs (except for nausea and vomiting as well as AEs unrelated to treatment) the dose should be reduced according to the Cisplatin/Carboplatin Dose Level Table at the discretion of the investigator. Dose reductions for treatment day (or within 2 days of treatment) ANC and platelet counts should also be made according to the Dose Level Table below.

NOTE: The etoposide will be held if platinum is held until a decision is made to skip platinum for the current cycle so that all drugs are kept on the same schedule.

- **Discontinuation** Also, except for nausea and vomiting, if any of the same non-hematologic grade 3 and 4 AEs that are at least possibly related to platinum recur after two reductions for that AE, then platinum will be stopped.
- A patient's protocol treatment will be discontinued if more than 2 cumulative dose reductions are necessary or if patients are unable to restart platinum within 3 weeks of interruption. Dose reductions will be permanent. Missed doses will be made up once toxicity is resolved per guidelines below.
- All toxicity grades below are described using the NCI Common Terminology Criteria for Adverse Events (CTCAE) version 4.0.

Cisplatin Dose Level Table	
Dose Level	Dose in mg/m ² (days 1-3)
0	25
-1	20
-2	16

*Note this is a 20% dose reduction with each dose level.

Carboplatin Dose Level Table	
Dose Level	Dose in AUC (day 1)
0	5
-1	4

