Grade 3 (ANC < 1.0 x 10 ⁹ /L, single temperature of > 38.3°C or a sustained temperature of ≥ 38.0°C)	Omit dose of cisplatin, then - If resolved by ≤ 7 days, then ↓ 1 dose level and consider prophylactic growth factor support per ASCO guidelines. - If not resolved within 7 days despite appropriate management including full clinically indicated course of antibiotics, if indicated, discontinue patient from study treatment.	Omit dose of carboplatin, then - If resolved by ≤ 7 days, then ↓ 1 dose level and consider prophylactic growth factor support per ASCO guidelines. - If not resolved within 7 days despite appropriate management including full clinically indicated course of antibiotics, if indicated, discontinue patient from study treatment.
Grade 4	Discontinue study treatment.	Discontinue study treatment.
Platelet count decreased (Thrombocytopenia)		
Grade 1 (PLT < LLN - 75 x 10 ⁹ /L)	Omit dose of cisplatin until resolved to CTCAE Grade ≤ 1, then maintain dose level	Omit dose of carboplatin until resolved to CTCAE Grade ≤ 1, then maintain dose level
Grade 2 (PLT < 75 - 50 x 10 ⁹ /L)	Omit dose of cisplatin until resolved to CTCAE Grade ≤ 1, then ↓ 1 dose level	Omit dose of carboplatin until resolved to CTCAE Grade ≤ 1, then ↓ 1 dose level
Grade 3 (PLT < 50 - 25 x 10 ⁹ /L)	Omit dose of cisplatin until resolved	Omit dose of carboplatin until

Worst Toxicity CTCAE v4.0 Grade (unless otherwise specified)	Recommended Dose Modifications to cisplatin any time during a cycle of therapy	Recommended Dose Modifications to carboplatin any time during a cycle of therapy
	to CTCAE Grade \leq 1, then - If resolved in \leq 7 days, then then ↓ 1 dose level. - If resolved in $>$ 7 days, then discontinue study treatment.	resolved to CTCAE Grade \leq 1, then - If resolved in \leq 7 days, then then ↓ 1 dose level. - If resolved in $>$ 7 days, then discontinue study treatment.
Grade 4 (PLT $<$ 25 x 10 ⁹ /L)	Discontinue study treatment.	Discontinue study treatment
Bleeding		
Any bleeding (related to cisplatin or carboplatin) resulting in a transfusion requirement	Omit dose of cisplatin until no further bleeding has been observed. Continuation of study treatment may be considered.	Omit dose of carboplatin until no further bleeding has been observed. Continuation of study treatment may be considered.
INVESTIGATIONS – RENAL		
Serum creatinine		
Grade 1 ($>$ ULN - 1.5 x ULN)	Maintain dose level.	Maintain dose level

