Grade 2 ($>$ 1.5 - 3.0 x ULN)	Omit dose of cisplatin until resolved to CTCAE Grade \leq 1 or baseline, then - If resolved in \leq 7 days, then maintain dose level. - If resolved in $>$ 7 days, then ↓ 1 dose level.	Omit dose of carboplatin until resolved to CTCAE Grade \leq 1 or baseline, then - If resolved in \leq 7 days, then maintain dose level. - If resolved in $>$ 7 days, then ↓ 1 dose level.
Grade \geq 3 ($>$ 3.0 x ULN)	Discontinue study treatment.	Discontinue study treatment
INVESTIGATIONS – HEPATIC		
Blood Bilirubin ^b (for patients with Gilbert Syndrome these dose modifications apply to changes in direct bilirubin only) For patients with total bilirubin \geq grade 3, a CT scan or equivalent imaging procedure to exclude disease progression or potential other liver disease should be performed.		
Grade 1 ($>$ ULN – 1.5 x ULN)	Maintain dose level.	Maintain dose level
Grade 2 ($>$ 1.5 – 3.0 x ULN)	Omit dose of cisplatin until resolved to CTCAE Grade \leq 1, then - If resolved in \leq 7 days, then maintain dose level. - If resolved in $>$ 7 days, then ↓ 1 dose level.	Omit dose of carboplatin until resolved to CTCAE Grade \leq 1, then - If resolved in \leq 7 days, then maintain dose level. - If resolved in $>$ 7 days, then ↓ 1 dose level.
Grade 3 ($>$ 3.0 – 10 x ULN) or higher	Discontinue study treatment. NOTE: If CTCAE Grade 3 or 4 hyper-bilirubinemia is due to the indirect (non-conjugated) component only, and hemolysis as the etiology has been ruled out as per institutional guidelines (e.g. review of peripheral blood smear and haptoglobin determination), then ↓ 1 dose level and continue treatment at the discretion of the Investigator.	Discontinue study treatment. NOTE: If Grade 3 or Grade 4 hyperbilirubinemia is due to the indirect (unconjugated) component only, and hemolysis as the etiology has been ruled out as per institutional guidelines (e.g., review of peripheral blood smear and haptoglobin determination), then ↓ 1 dose level and continue treatment at the discretion of the investigator.
AST or ALT		

Worst Toxicity CTCAE v4.0 Grade (unless otherwise specified)	Recommended Dose Modifications to cisplatin any time during a cycle of therapy	Recommended Dose Modifications to carboplatin any time during a cycle of therapy
Grade 1 and 2 (up to 5.0 x ULN)	Maintain dose level.	Maintain dose level.

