Worst Toxicity CTCAE v4.0 Grade (unless otherwise specified)	Recommended Dose Modifications to cisplatin any time during a cycle of therapy	Recommended Dose Modifications to carboplatin any time during a cycle of therapy
Grade 2	Omit dose of cisplatin until resolved to CTCAE Grade ≤ 1, initiate anti-emetic treatment, then maintain dose level.	Omit dose of carboplatin until resolved to CTCAE Grade ≤ 1, initiate anti-emetic treatment, then maintain dose level.
Grade 3	Omit dose of cisplatin until resolved to CTCAE Grade ≤ 1, initiate anti-emetic treatment, then: - If resolved in ≤ 48 hours, maintain dose level. - If resolved in > 48 hours, then ↓ 1 dose level.	Omit dose of carboplatin until resolved to CTCAE Grade ≤ 1, initiate anti-emetic treatment, then: - If resolved in ≤ 48 hours, maintain dose level. - If resolved in > 48 hours, then ↓ 1 dose level.
Grade 4	Discontinue study treatment.	Discontinue study treatment.
GENERAL DISORDERS		
Fatigue		
Grade 1 or 2	Maintain dose level.	Maintain dose level.
Grade 3	Omit dose of cisplatin until resolved to CTCAE Grade ≤ 1, then - If resolved in ≤ 7 days, maintain dose level. - If resolved in > 7 days, discontinue patient from study treatment.	Omit dose of carboplatin until resolved to CTCAE Grade ≤ 1, then - If resolved in ≤ 7 days, maintain dose level. - If resolved in > 7 days, discontinue patient from study treatment.
Grade 4	Discontinue study treatment.	Discontinue study treatment.
INFUSION REACTIONS		
Infusion reactions		
Grade 1 (Transient flushing or rash, fever < 38 °C [$<100.4^{\circ}\text{F}$]; intervention not indicated)	
 - Stop infusion - Treat per institutional guidelines. - May resume infusion (within 4 hours of initial start of infusion) at 50% of previous under continuous observation. Ensure that there is a minimum observation period of 1 hour prior to restarting the infusion. - Maintain dose level. - If the AE recurs at the reinitiated slow rate of infusion, and despite oral pre-medication, then do not resume infusion. 	
 - Stop infusion - Treat per institutional guidelines. - May resume infusion (within 4 hours of initial start of infusion) at 50% of previous under continuous observation. Ensure that there is a minimum observation period of 1 hour prior to restarting the infusion. - Maintain dose level. - If the AE recurs at the reinitiated slow rate of infusion, and despite oral pre-medication, then do not resume infusion.

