5.3.5.2 Non-hematologic Toxicity

Gastrointestinal Toxicity, Nausea and Vomiting

All patients should receive antiemetics* to prevent nausea and vomiting. Steroids and 5-HT3 antagonists are required premedications but additional specific antiemetic therapy is left to the discretion of the treatment physician. If vomiting is severe, consider hospital admission and/or use of aprepitant if possible. Do not modify chemotherapy doses.

*Aprepitant, when given once daily for 14 days as a 100 mg capsule with an oral contraceptive containing 35 mcg of ethinyl estradiol and 1 mg of norethindrone, decreased the AUC of ethinyl estradiol by 43% and decreased the AUC of norethindrone by 8%. Women of childbearing potential using pregnancy contraception that includes ethinyl estradiol should not receive Aprepitant for the treatment of nausea/delayed emesis. Patients may change to a different method of contraception if they wish to use Aprepitant.

Hepatotoxicity

Bilirubin	Etoposide*
≤ 1.5 X ULN	100%
> 1.5 – 3.0 X ULN	50%
> 3.0 X - ≤ 5.0 ULN	30%
> 5 X ULN	Hold**

* Please note that the % dose administered is based on the original starting dose of etoposide (100 mg/m²). If patient is at dose level -1 or -2, % should be based on reduced dose the patient is currently on, not original dose.

** For bilirubin greater than 5 X ULN it is recommended not to use etoposide for that cycle but this is at the discretion of the treating physician. If holding, repeat labs on a weekly basis for

up to 3 weeks until total bilirubin is \leq 5 X ULN. The cisplatin dose should also be held if etoposide is held so that all drugs are kept on the same schedule. If bilirubin improves within 3 weeks to \leq 5 X ULN, then resume treatment and use reduced dose per table above. If bilirubin does not improve to \leq 5 X ULN within 4 weeks, discontinue protocol therapy.

Hypomagnesemia

Hypomagnesemia is not an indication for stopping therapy. Oral or parenteral magnesium supplementation is indicated for serum magnesium levels $<$ 1.5 mEq/L.

Allergic Reactions

Discontinue all protocol treatment promptly if \geq grade 3 anaphylaxis develops.

Suggested Management of Allergic Reaction:

In case of mild allergic symptoms (e.g., appearance of a localized or generalized pruritus), symptomatic treatment may be given (e.g., oral antihistamine or corticosteroids).

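### Arm B's general, platinum and etoposide dose-modification sections conflict on at least five topics, including stop versus continue for the same severe toxicity, and no section is said to govern

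*Combined protocol and SAP*

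**What the plan says.** Section 5.3.4.1 (platinum table) sets modifications by worst grade at any time in a cycle. Sections 5.3.5.1 and 5.3.5.2 set them for etoposide, with some statements that reach all drugs. Section 5.3.1 gives general rules.

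- **Platelets.** At "Grade 4 (PLT $<$ 25 x 10 ⁹ /L", 5.3.4.1 ends study treatment for both platinum agents. At the same threshold, the thrombocytopenia paragraph of 5.3.5.1 says "the dose of Etoposide should be reduced by one dose level according to the Etoposide Dose Level Table for the next cycle" and for all cycles after it.
- **Bilirubin.** At "Grade 3 ($>$ 3.0 – 10 x ULN) or higher", 5.3.4.1 ends study treatment, except for a purely indirect elevation with hemolysis excluded. Section 5.3.5.2 gives 30% of etoposide above 3 and up to 5 x ULN. Above 5 x ULN it advises a hold, at the physician's discretion, and on recovery within 3 weeks "then resume treatment and use reduced dose per table above".
- **Vomiting.** The grade 3 nausea/vomiting row of 5.3.4.1 says "If resolved in > 48 hours, then ↓ 1 dose level", and grade 4 ends study treatment. Section 5.3.5.2 says of severe vomiting "Do not modify chemotherapy doses". The lead-in to 5.3.4 applies its grade 3–4 reduction rule "except for nausea and vomiting as well as AEs unrelated to treatment".
- **Febrile neutropenia.** Section 5.3.4.1 says for grade 3 "If not resolved within 7 days despite appropriate management including full clinically indicated course of antibiotics, if indicated, discontinue patient from study treatment", and grade 4 also ends study treatment. Section 5.3.5.1 lowers cisplatin and etoposide by one level for later cycles when IV antibiotics are needed and ANC is below 500/mm³. Carboplatin is not named.
- **Missed doses.** Section 5.3.1 says they are not made up; 5.3.4 says they are, once toxicity resolves.
- **Other grade 4 non-hematologic toxicity.** The last rows of 5.3.4.1 end study treatment. Section 5.3.5.2 holds all therapy, permits restart after resolution to below grade 1, and then reduces etoposide.

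**The concern.** Etoposide is given in this trial only with a platinum agent, so a patient who meets a rule in 5.3.5 normally falls under the platinum table as well. Where one section ends study treatment and another assumes further cycles, the site has two instructions for one event and must choose. Two patients with the same severe toxicity may then be managed differently, one taken off treatment and the other given more cytotoxic therapy. A monitor or the data safety monitoring committee has no single rule against which to judge a deviation.

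These events are foreseeable. Section 8 lists thrombocytopenia and neutropenia for carboplatin, and severe vomiting in almost all cisplatin patients without adequate prophylaxis.

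**Working it through.** There is no sample-size or power figure to reproduce. The check is a side-by-side reading by event, followed by a search for any rule that would settle the differences.

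| Event in Arm B | Sections 5.3.1 / 5.3.4 / 5.3.4.1 | Section 5.3.5 | Both can be carried out? |
|---|---|---|---|
| Platelets < 25 x 10^9/L | Stop study treatment | Etoposide down one level, next and all later cycles | No |
| Bilirubin > 3 x ULN, not indirect-only | Stop study treatment | 30% etoposide, or hold and resume | No |
| Vomiting, grade 3 for > 48 h, or grade 4 | Platinum down one level; stop at grade 4 | Leave chemotherapy doses unchanged | No |
| Febrile neutropenia, ANC < 500/mm³, IV antibiotics, grade 4 or grade 3 unresolved at 7 days | Stop study treatment | Cisplatin and etoposide down one level, continue | No |
| Other treatment-related grade 4 non-hematologic event | Stop study treatment | Hold, restart, reduce etoposide | No |
| Missed doses | 5.3.1: not made up; 5.3.4: made up | – | No |

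**Count.** Six topics. Setting aside any one leaves 6 − 1 = 5.

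**Do the febrile neutropenia definitions overlap?** Section 5.3.4.1 uses ANC < 1.0 x 10^9/L with a single temperature above 38.3 °C or a sustained temperature of at least 38.0 °C. Section 5.3.5.1 uses ANC < 500/mm³ and a temperature above 100.5 °F. Since 38.3 x 9/5 + 32 = 100.94 °F, a patient with ANC < 500/mm³, a single reading above 38.3 °C and IV antibiotics meets both. For IV-treated grade 3 cases resolved within 7 days the two sections agree for cisplatin. Fever treated successfully with oral antibiotics is a further mismatch: 5.3.5.1 makes no adjustment, while 5.3.4.1 lowers platinum one level after any grade 3 event resolved within 7 days.

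**Bilirubin.** The etoposide table has four bands: ≤ 1.5, > 1.5–3.0, > 3.0–5.0 and > 5 x ULN. Two of the four lie above 3.0, where 5.3.4.1 stops study treatment. If 5.3.4.1 is followed as written, those two bands are left for the indirect-only exception. Otherwise, in the > 3.0–5.0 band, the choice is between no further treatment and 30% of the current etoposide level:

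- level 0: 0.30 x 100 = 30 mg/m²
- level −1: 0.30 x 80 = 24 mg/m²
- level −2: 0.30 x 64 = 19.2 mg/m²

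**Is there a precedence rule?** Two texts come close.

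1. Section 5.3.1 says to take the larger reduction when two different toxicities call for different percentage reductions of one drug. It does not cover one toxicity with two instructions, or stop versus continue.
2. The closing note of 5.3.4.1 calls the table general guidance and lets the investigator omit, reduce or stop. It does not say whether 5.3.4.1 or 5.3.5 governs. The same note makes its delay limit of more than 21 days mandatory.

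**Time limits (clarity only, not in the count).** Platinum must restart within 3 weeks (5.3.4), or delay may not exceed 21 days (5.3.4.1). Section 5.3.1 stops at 4 weeks or more. Sections 5.3.5.1 and 5.3.5.2 each use both 3 and 4 weeks. In the 5.3.5.2 bilirubin text, recovery within 3 weeks leads to resumption and no recovery within 4 weeks leads to a stop. First recovery on days 22–28 (28 − 21 = 7 days) has no instruction in that paragraph.

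**The case against.** The best reply is that most of these are not strict contradictions. A site that stops under 5.3.4.1 breaches nothing in 5.3.5, because the etoposide reduction applies only if there is a next cycle. On that reading only vomiting and missed doses truly clash. But no sentence tells sites to take the stricter instruction, and a site that follows 5.3.5 in good faith departs from 5.3.4.1. The reading also leaves the grade 4 platelet paragraph of 5.3.5.1 with almost nothing to govern, since Arm B patients receive both drugs. The same reasoning applies to the time limits, which is why they are not counted.

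A second reply is that the rules are drug-specific. The table speaks of omitting cisplatin or carboplatin when it means one agent, but of study treatment in the contested rows. Section 5.3.5 also reaches across drugs for fever, vomiting and the bilirubin hold. Section 5.3.1 expressly allows one agent to be dropped and the other continued only for Arm A.

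Several narrower points have force:

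- Missed doses could be read as a general rule with a platinum-specific exception, though the text does not say so.
- The exemption in 5.3.4 could hand vomiting over to the table's own rows, so the firm conflict is 5.3.4.1 against 5.3.5.2.
- Toxicity unrelated to treatment is exempt from reduction, and it is unstated whether the bilirubin stop covers such cases. The two upper etoposide bands may therefore have some use beyond the indirect-only exception.
- The day 22–28 gap is partly closed by the 3-week and 21-day platinum limits when platinum is also held.
- The guidance label and investigator discretion soften the platinum rows.

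None of these says which section prevails.

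**Conclusion.** The concern holds. The current protocol text conflicts on six topics, and at least five remain if any single one is discounted. For platelets, bilirubin, febrile neutropenia and other grade 4 toxicity, one section ends study treatment and another continues it. For vomiting, reduction or discontinuation is set against no change. For missed doses, the statements are opposite. This rests on reading study treatment in 5.3.4.1 as all Arm B therapy, which fits that table's separate wording for single drugs.

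The documents do not allow a count of affected patients. No bias in PFS and no loss of power is claimed, because Section 5.6 follows patients who stop early until progression. The point should still be fixed before further conduct, because it concerns severe toxicity of cytotoxic drugs. No view is taken on which rule is clinically right.

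**What to change.** Amend Sections 5.3.1, 5.3.4/5.3.4.1 and 5.3.5 together:

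1. For each of the six topics, make the platinum and etoposide texts give one consistent instruction. Drug-specific rules may stay if they are compatible.
2. Cover carboplatin explicitly wherever 5.3.5 names only cisplatin, and use one definition of febrile neutropenia, including cases treated with oral antibiotics.
3. Make the missed-dose statements and the 3- and 4-week limits agree, including recovery of bilirubin between days 22 and 28.
4. State which section takes precedence if a difference remains, and which rows of the platinum table are mandatory and which are guidance.

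The clinical leads choose the rules. The cost is protocol amendment wording and a memo to sites. Sample size, endpoints and analysis are unchanged.
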